
關鍵詞 (Keywords) : COVID-19, Long COVID, long-term effects, mixed-methods, health-related quality of life, longitudinal cohort study

Aims

The overarching goal of this proposed project is to explore the Long COVID and associating factors in Taiwan. In the proposed research project, we intend to investigate both ongoing and post-COVID-19 syndrome defined by NICE guideline and referred these symptoms as Long COVID. Building upon the overarching goal, the specific aims of this research project are to (1) integrate the state of science of Long COVID, (2) describe the changes of various symptoms and HRQOL after 3, 6, 9, and 12 months of COVID-19 diagnosis, (3) explore predicting factors of the existence and severity of Long COVID, and (4) explore how patient experienced COVID-19 symptoms.

Introduction

Starting from the beginning of 2020, the COVID-19 pandemic has already affected more than one billion people with over three million deaths globally [1]. In Taiwan, about ten thousands covid-19 cases were confirmed in mid-June, 2021, and the case number continues to grow [2]. While a lot of individuals diagnosed with COVID-19 completed the treatment course of the acute phase and returned to their community, a considerable portion of COVID-19 survivors continuously experienced complicated, distressing, and multiple long-term symptoms weeks to months after COVID-19 diagnosis [3, 4]. These long-term symptoms sometimes may be labeled as Long COVID, post-COVID symptoms, or ongoing symptoms and have profound impact on individuals health, function, and quality of life [5, 6]. Thus developed guidelines stress the importance of monitoring and managing Long COVID continuously [7]. However, the symptom profile is still vague and the guideline is left to be scrutinized.

Symptom profile of Long COVID

Although it is expected that the acute symptoms of COVID-19 last about a week [8], researchers have warned that more than 50 long-term symptoms or signs can be experienced by COVID-19 survivors weeks after diagnosis [3].

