These evidence of long-term organ damage, symptom burden, and functional impairment lead healthcare providers to wonder if it is possible to predict who will develop Long COVID. While results from some studies showed that the severity of acute COVID-19 symptoms associate with Long COVID [6, 15], a study pointed out that there is no relationship between disease severity and chronic fatigue post COVID recovery [9]. Instead, female and history of psychological distress may associate with prolonged fatigue [9]. Another study recruited more than four thousand patients in UK found that older age, increasing BMI, female sex, and experiencing more than five symptoms during the first week of illness were associated with Long COVID [16]. In a similar vein, female sex and overweight/obesity were found to be related to lower HRQOL in survivors [13]. In short, the severity of acute symptoms, preexisting comorbidity, female gender, and BMI or weight are all potential predictors of Long COVID [6, 9, 13, 15, 16]. With that being said, current evidence is premature to determine what can predict the existence or severity of Long COVID at different stage of survivorship.

-Guideline for Current Practice

In order to managing Long COVID, National Institute for Health and Care Excellence (NICE), the Scottish Intercollegiate Guidelines Network (SIGN), and the Royal College of General Practitioners (RCGP) published a rapid guideline in December, 2020 [17]. In this NICE guideline, symptoms of COVID-19 are categorized as acute (i.e., signs and symptoms for up to 4 weeks), ongoing (i.e., signs

and symptoms from 4 to 12 weeks), and post-COVID-19 syndrome (i.e., signs and symptoms continue for more than 12 weeks and are not explained by an alternative diagnosis). It recommends that healthcare providers should be aware of possible symptoms, actively discuss with survivors in terms of their symptom experience and how symptoms affect their function and life, offer chest X-ray by 12 weeks after acute COVID-19, offer an exercise tolerance test, and consider referring survivors to an integrated multidisciplinary assessment. It also stressed the importance of long-term follow-up with symptom changes. However, upon the time of guideline development, accessible evidence was still scarce and of poor quality [7]. Furthermore, while the guideline repeatedly mentioned the needs to discuss symptom impacts on function and life, relevant reference is even less available.

The Knowledge Gap

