Taken it together, evidence has strongly supported the profound impact of Long COVID. However, there is still a huge knowledge gap regarding the trajectory, impacts, predictors, and interventions of Long COVID. For example, with regard to the symptom trajectory, most studies measured Long COVID at one time point, ranged from 14 to 180 days without defining ongoing and post-COVID-19 syndrome clearly [3, 4]. Less study observed symptom trajectory overtime. No evidence of symptom profile after 6 months of diagnosis is available. The way to identify symptoms also varies. Researchers selected various instruments or pre-determined lists of symptoms without clear rationale. Some research used chart review to identify symptoms. It is possible that some symptoms were ignored if they were not on the lists or does not documented in the medical record.

While emerging studies addressed the impacts of Long COVID on HRQOL and function, relevant data is still insufficient, including the HRQOL and function changes over time. To our knowledge, there is no qualitative studies describing symptom experience from survivors' perspectives. The changes of HRQOL and function is an important information for decision making of selecting palliative care and assessing rehabilitation needs. Lastly, most studies were completed in certain areas, such as US, UK, and other regions of Europe.

When "a worrying new wave of COVID-19 is hitting South-East Asia" [18], including Taiwan, it is imperative to follow up with these patients' symptom trajectory and experience comprehensively in order to monitor symptom burdens, identify needs, and manage symptoms early.

Methods

This is a **three-phase, mixed-methods research project with embedded design** (Figure 1.). Mixed-methods design is selected because it allows us to

comprehend the phenomenon from multiple aspects—the lack of information regarding longitudinal aspects and survivors' aspects is identified in the previous paragraphs. The following bullet points describe the embedded design according to the six key characteristics which are used to categorize and understand different mixed-methods designs [19].

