1. Number of study phases, type of implementation process, and stage of integration of approaches: The proposed project include three phases. Following the first phase of preparation, **phase two (quantitative strand) and three (qualitative strand) are conducted concurrently**. The integration of quantitative and qualitative findings happens in the end of the whole projects to triangulate qualitative and quantitative findings.
2. Theoretical perspective: The embedded design includes dealing with both quantitative and qualitative data and is supported by the pragmatism worldview. The pragmatism perspective appreciates both singular and multiple realities and emphasizes practicality. Pragmatism embraces abduitive logic and is research question centered [20].
3. Function of the research study: The embedded design allow us to enhance the overall design of the quantitative, cohort study by adding qualitative approach. It is an important strategy as the interested phenomenon is not clearly understood and may be missed if we only use quantitative methods to explore.
4. Priority of methodological approach: Quantitative method is the primary part of this study.

Study procedure

In the first phase, a systematical review will be conducted to address research aim one. The second and third phase will cover quantitative strand and qualitative strand, respectively. The quantitative strand will employ cohort study design to follow up with COVID-19 survivors regularly for a year (aim 2 and 3). The qualitative design will explore their symptom experience (aim 4).

-Phase two: Quantitative strand

The independent variables for the cohort study of the quantitative strand are demographic variables (e.g., age, sex, chronic disease, smoking, BMI) and symptom severity at COVID-19 diagnosis. The dependent variables are existence and severity of Long COVID symptoms and several indicators of health status, including known infection episodes, fever, SpO₂ level, hospital or emergency room admissions, and any new diagnosis.

[figure not shown]

Figure 1. Two Phases Mixed Methods Research Design

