Sampling and Recruitments. Inclusion criteria are individuals who are (1) at least 20 years-old and (2) diagnosed with COVID-19 within six months. Exclusion criteria are individuals who (1) are still in the active phase of COVID-19 infection (i.e., diagnosed within 4 weeks) and (2) have cognitive impairment or other issues that prevents them from doing self-ratings of symptoms via phone interviews. The estimated sample size is about 98 subjects based on G*Power 3.1.9.4 calculation (effect size $f^2=0.15$, $\alpha=0.05$, $\beta=0.2$, 6 predictors). Considering the loss of follow-up rate of 20%, 118 subjects are needed.

Potential subjects will be identified through the following strategies: (1) searching the intranet of participating medical institutions (e.g., National Taiwan University Hospital, National Yang Ming Chiao Tung University Hospital and Min-Sheng General Hospital), (2) recruitment messages posting on social media, and (3) referrals from collaborating healthcare providers. After participants fill out the online questionnaire, research assistant will approach potential subjects via phone to explain the research, explore their willingness, and screen for eligibility. Individuals who are eligible and agree to participate in the study will receive documents of study information and consent form by mail. Participants are required to mail back the signed inform consents.

Upon the receiving the signed inform consents, the subjects will be followed immediately to confirm participation and collect demographic data. They will then be regular followed up at 3 (for those who are participated within 3 months of COVID diagnosis), 6, 9, and 12 months (T1-4) from the diagnosis of COVID-19. During these regular follow-ups, subjects will need to report health status indicators and rate their symptom severity and HRQOL based on selected instruments. Subjects will have access to a line group managed by the research team. They can communicate with the research team regarding any issues of research or symptoms through line group. All data collection will be occurred via online questionnaire, phone or video call interview (e.g., +Google meet or line video call). Paper documents, such as inform consents, will be stored in the locked cabin located at National Taiwan University School of Nursing. Electrical data will be managed and stored using Redcap and encrypted Dropbox.

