Statistical methods. In addition to use descriptive statistics to describe the characteristics of participants and symptoms, one-way repeated measures analysis of variance (ANOVA) will be employed to determine whether there are any differences of symptom severity along the four time points (aim 2). Binomial logistic regression will be selected to predict a dichotomous dependent variable (i.e., existence of Long COVID) given multiple independent variables. Multiple linear regression will be used to predict continuous dependent variable (i.e., symptom severity) given multiple independent variables (aim 3).

Table 1. Long COVID Symptoms Mentioned by Example Studies and Instruments

First Author of the Studies or Instrument	Lopez-Leon	Romero-Duarte	EORTC-QLQ30	LC29
Fatigue	58%	22-34%	V	-
Pain	11%	-	V	V
Joint pain/ muscular pain	19%	15.3%	-	V
Muscle weakness	-	3.8%	-	V*
Weight loss	17%	-	-	V
Alopecia	25%	3%	-	V
Red eyes	6%	-	-	V
Cutaneous signs	12%	1.5-3.1%	-	V
Dyspnea	24%	28%	V	V
Polypnea	21%	-	-	V
Cough	19%	19.2%	-	V
Throat pain	3%	8.4%	-	V
Chest discomfort	16%	6.6%	-	V
Rib pain	-	4.5%	-	V
Headache	44%	5.3%	-	V*
Anosmia/ loss of the sense of smell	21%	-	-	-
Ageusia/ loss of the sense of taste/ dysgeusia	23%	7.2%	-	-
Paresthesia	-	3.4%	-	V
Attention disorder	27%	-	V	-
Memory loss	16%	-	V	-
Dizziness	3%	1.9%	-	V
Depression	12%	4.4%	V	-
Anxiety	13%	6.8%	V	-
Mood disorder	2%	-	V	-
Dysphoria	2%	-	-	-
Sleep disorder	11%	4.9%	V	-
Palpitation	11%	3.1%	-	-
Diarrhea	-	10.3%	V	
Constipation	-	1.8%	V	-
Abdomen pain	16%	5.4%	-	V*
N/v	58%	2%	V	-
Anorexia	11%	1%	V	-

Note. Table 1 compares the Long COVID symptoms mentioned by example studies and selected instruments. The percentage represents how many people have reported specific symptoms in the study. The check mark represents symptoms addressed in the instrument. Grey shading highlights symptoms that are not covered by EORTC QLQ30 or LC29. The instrument uses different terminology to describe the symptom.

Qualitative strand

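### The Long COVID outcome in Aim 3 has no operational rule, and no described item separates symptoms that are new or worse since COVID-19 from background or otherwise explained ones

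*Combined protocol and SAP*

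**What the plan says.** All references are to the combined protocol and SAP.

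- **Outcome.** Statistical methods: "Binomial logistic regression will be selected to predict a dichotomous dependent variable (i.e., existence of Long COVID) given multiple independent variables". A multiple linear regression of symptom severity accompanies it. Neither sentence says which symptoms enter, what rating counts, how many symptoms make a case, or which visit is used.
- **Definition.** Aims: "we intend to investigate both ongoing and post-COVID-19 syndrome defined by NICE guideline and referred these symptoms as Long COVID". Guideline for Current Practice describes the later of these categories as one where "symptoms continue for more than 12 weeks and are not explained by an alternative diagnosis".
- **Timing.** Sampling and Recruitments sets ratings at 3 months (for those who join early enough) and at "6, 9, and 12 months (T1-4) from the diagnosis of COVID-19".
- **Data at follow-up.** In the same section, "subjects will need to report health status indicators and rate their symptom severity and HRQOL based on selected instruments". Under Instruments, these are the QLQ-C30, 22 items of the LC29, and a presence check for loss of smell, loss of taste and palpitation.
- **Data on other causes.** Phase two lists as predictors "demographic variables (e.g., age, sex, chronic disease, smoking, BMI) and symptom severity at COVID-19 diagnosis", and among the outcomes "hospital or emergency room admissions, and any new diagnosis". Both chronic disease and new diagnosis are recorded per person, not per symptom.
- **The plan's own standard.** The Knowledge Gap faults earlier studies for measuring Long COVID "without defining ongoing and post-COVID-19 syndrome clearly".

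**The concern.** The symptoms rated include fatigue, pain, dyspnoea and poor sleep, which people also have for reasons unrelated to COVID-19. The adopted definition deals with this by excluding symptoms that another diagnosis accounts for. The data collection, as described, gives no means of applying that exclusion symptom by symptom. It also describes no pre-COVID rating and no comparison group from which a background level could be judged.

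Followed as written, a symptom that predates COVID-19 or has another cause can count as Long COVID. Chronic disease is both a likely source of such symptoms and a listed predictor, so the error would differ between the groups that the model compares. Expecting outcomes intends the predictors to pick out high-risk people early, so a false predictor would matter. Onset and attribution that were not asked about cannot be recovered at analysis.

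**Working it through.** **1. The definition set against the data described**

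| The definition needs | The plan describes | Gap |
|---|---|---|
| A symptom is present | Current ratings on 4-point items; presence check for three symptoms | No symptom set, cut-off or number of symptoms |
| Time since diagnosis | Visits at 3, 6, 9 and 12 months | Timing is known; the visit used in the model is not stated |
| No other diagnosis accounts for it | Chronic disease and new diagnosis, per person | Not linked to any symptom |
| It follows from COVID-19 | Severity at diagnosis, as a predictor | No new-or-worse item, no pre-COVID rating, no comparison group |

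Three months is about 13 weeks (52/4), so the scheduled ratings fall in the category that carries the exclusion.

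**2. Logistic model**

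The documents give no background rates and no cut-off, so every input here is assumed. Let b be the probability of a background symptom and p the probability of a COVID-caused one. Assume the two are independent and every COVID-caused case is detected. Then the observed rate is q = 1 − (1 − b)(1 − p), and OR = [q1/(1 − q1)] / [q0/(1 − q0)].

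*Spurious association.* Here p is the same with and without chronic disease, so the true OR is 1.0. Example with b = 0.20 vs 0.40 and p = 0.30: q0 = 1 − 0.80 × 0.70 = 0.44; q1 = 1 − 0.60 × 0.70 = 0.58; OR = (0.58/0.42)/(0.44/0.56) = 1.76.

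| b without vs with chronic disease | OR, p = 0.10 | OR, p = 0.30 | OR, p = 0.50 |
|---|---|---|---|
| 0.05 vs 0.10 | 1.38 | 1.17 | 1.11 |
| 0.10 vs 0.20 | 1.66 | 1.34 | 1.23 |
| 0.20 vs 0.40 | 2.19 | 1.76 | 1.56 |
| 0.30 vs 0.50 | 2.08 | 1.78 | 1.62 |

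*Attenuation.* Here b is the same in both groups and the true OR is 2.0. Example with p0 = 0.30: odds 2 × 0.30/0.70 = 0.857, so p1 = 0.4615. With b = 0.30, q0 = 0.51 and q1 = 0.623, and the observed OR is 1.59.

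| p0 | Observed OR, b = 0.10 | Observed OR, b = 0.30 |
|---|---|---|
| 0.10 | 1.53 | 1.27 |
| 0.30 | 1.81 | 1.59 |
| 0.50 | 1.91 | 1.77 |

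*Spill-over to age.* Assume chronic disease in 20% of younger and 50% of older people, background depending on chronic disease only, and no COVID effect of either. Example with b = 0.20 vs 0.40 and p = 0.10: q is 0.28 without and 0.46 with chronic disease. Younger: 0.8 × 0.28 + 0.2 × 0.46 = 0.316. Older: 0.5 × 0.28 + 0.5 × 0.46 = 0.37. Crude OR = (0.37/0.63)/(0.316/0.684) = 1.27. Over all four background pairs and three values of p, the crude age OR runs from 1.03 to 1.27. Adjusting for chronic disease returns it to 1.00, because the rate within each stratum does not depend on age. The chronic-disease OR itself is unchanged.

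**3. Linear severity model**

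Assume background and COVID-caused severity add.

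- *Predictor linked to background.* If background adds one category on a 4-point item in 20% vs 40% of people, the chronic-disease coefficient shifts by 0.40 − 0.20 = 0.20 points with no COVID effect.
- *Predictor unrelated to background.* Background adds the same mean m to both groups, and (μ1 + m) − (μ0 + m) = μ1 − μ0. The coefficient is not attenuated; the cost is precision. The plan's sample size of 98 reproduces from the overall F test (f² = 0.15, 6 predictors, α = 0.05; power 0.8035 at N = 98 and 0.7984 at N = 97). R² is then 0.15/1.15 = 0.130. If background adds 25%, 50% or 100% to the outcome variance, f² falls to 0.117, 0.095 or 0.070, and power at N = 98 falls to 68%, 57% or 43%.

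**4. Frequency**

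With p = 0.30 and every true case detected, the observed rate is 0.335 to 0.51 without and 0.37 to 0.65 with chronic disease. If a strict cut-off detected only half of true cases (0.15) and b = 0.10, it would be 1 − 0.90 × 0.85 = 0.235, below the true 0.30.

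**The case against.** **A definition exists.** The plan names the NICE categories, so a reader who infers that Long COVID is left undefined goes too far. What is missing is the rule that turns ratings into a case. Two analysts could code the same 4-point answers differently and both cite NICE.

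**Chronic disease and new diagnoses are recorded.** They are, and adjusting for chronic disease removes the spill-over to age if age is linked to background only through it. Adjustment does not correct the chronic-disease coefficient, which is where the bias is largest.

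**The item may be on a form.** Appendices A and B and the recruitment and demographic forms were not available. This limit stands: the point concerns the data as described. The body of the plan presents the appendices as example questionnaires and mentions no onset or attribution question. Even if one exists, the outcome rule is still missing.

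**Aim 3 is exploratory.** That lowers the stakes, but Expecting outcomes still plans to use its predictors for early targeting.

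Four stronger readings are tempting and are not supported:

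- *Frequency is bound to be overstated.* That requires a lenient cut-off. None is stated, and a strict one could offset or reverse the error.
- *The linear coefficients are attenuated as the odds ratios are.* Under additive severities they are not.
- *Every predictor is biased.* One with no COVID effect and no link to background symptoms is unaffected.
- *Aim 2 fails too.* Symptom levels would include background, but a stable background does not by itself create change over time.

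**Conclusion.** The point holds for the plan as described. The Aim 3 binary outcome has no operational rule, and no described item applies the exclusion that the adopted definition requires beyond 12 weeks. Pre-existing or otherwise explained symptoms can therefore enter both Aim 3 outcomes. In the logistic model this can give chronic disease a spurious association and attenuate true odds ratios of other predictors. In the linear model it can shift the chronic-disease coefficient and cost precision elsewhere.

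The size cannot be derived from the documents. The ranges above illustrate it; they rest on assumed rates, independence of background and COVID-caused symptoms, and full detection of COVID-caused cases. The sponsor should make the change; it is not a reason to reject the design. Confidence is medium, because the size is unknown and the forms were not seen.

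**What to change.** 1. **Collect.** At each follow-up, for each symptom reported as present, ask whether it is new or worse since COVID-19 (yes/no). If yes, ask whether the participant has been told it is due to another condition (yes/no/not assessed).
2. **Prespecify.** State the symptom set, the rating that counts as present, the number of symptoms required, and the visit used for Aim 3.
3. **Name one primary definition:** at least the prespecified number of new-or-worse symptoms. Report two sensitivity versions: one excluding symptoms attributed elsewhere, and one counting all present symptoms.
4. **Severity.** Derive the severity outcome from the same symptoms as a parallel analysis.

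The version that excludes attributed symptoms should not be primary, because attribution may itself differ by chronic disease. If 10% vs 30% of true cases were attributed elsewhere (assumed), a true rate of 0.30 in both groups would be observed as 0.27 vs 0.21 (OR 0.72), and a true rate of 0.50 as 0.45 vs 0.35 (OR 0.66).

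**Cost.** One or two short answers per symptom present, on top of 30 + 22 + 3 = 55 items and the health-status questions. Someone with 5 symptoms gives at most 10 more answers. The burden is heavier for people with many symptoms, and Limitations already names retention as a challenge. The first question relies on recall of up to 12 months. Table 4 schedules data collection from October to December 2021, so visits completed before the items are added may lack them. State all three as limitations.

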Rather than just respiratory or localized symptoms, Long COVID seem to be more systematic [3, 4, 6]. The most frequent reported long-term symptoms across studies include fatigue (22-72%), respiratory symptoms (19-65.6%), neurological symptoms (7.2-44%), joint pain (15-19%), and psychological symptoms (4.4-46.9%) [3, 4, 6, 9]. Cardiovascular symptoms and GI symptoms were also reported [3, 4]. As studies surveyed Long COVID at different time points (from 3 weeks to 6 months) in various populations (e.g., hospitalized patients, individuals with mild, moderate, or severe acute symptoms), the incidence rate of Long COVID is between 20%-80% [3, 4, 6, 9].

While it seems that the symptoms gradually subsided over time [10], as

high as 30-40% of COVID survivors still experienced multiple symptoms at 6 months after diagnosis [4]. More importantly, these symptoms can be very frustrating. Although there is very little qualitative study described these survivors' experience or studies measured the intensity or distressing level of the persistent symptoms, some survivors have shared their horrible experience on internet [11, 12]. A 31-year-old female survivor commented that "nearly 12 months after I was first ill...I wanted to get out but I stood up and was so dizzy and breathless and so I couldn't even get dressed. [11]" Among few studies addressed health-related quality of life (HRQOL) in this population, their findings showed a significant drop in HRQOL, including impaired ability to perform daily activities, for a considerable number of COVID survivors [5, 6, 13].

In addition to the symptoms, findings from studies showed objective evidence of organ damage weeks to months after diagnosis. For example, abnormal chest x-ray, echocardiograms, elevated d-dimer, raised CRP, and lymphopenia were found and suggested lung and heart damage, clotting disorder, continuous inflammation, and reduced immunity [3, 14].

Predictors of Long COVID?

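### The sample size of 98 powers only the overall test of the linear severity model, at about 0.78 after the planned loss; it does not cover the logistic model for existence of Long COVID

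*Combined protocol and SAP*

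**What the plan says.** - **Aims** sets aim 3 as to "explore predicting factors of the existence and severity of Long COVID", without ranking the two. The opening of **Phase two: Quantitative strand** does the same: "The dependent variables are existence and severity of Long COVID symptoms and several indicators of health status".
- **Statistical methods** gives each its own model. For existence: "Binomial logistic regression will be selected to predict a dichotomous dependent variable (i.e., existence of Long COVID) given multiple independent variables". For symptom severity it plans multiple linear regression.
- **Sampling and Recruitments** holds the only calculation for the cohort: "The estimated sample size is about 98 subjects based on G*Power 3.1.9.4 calculation", with f² = 0.15, alpha 0.05, beta 0.2 and 6 predictors. It names neither the test nor the outcome. It then adds: "Considering the loss of follow-up rate of 20%, 118 subjects are needed".
- On what Long COVID is, **Aims** says "we intend to investigate both ongoing and post-COVID-19 syndrome defined by NICE guideline". **Guideline for Current Practice** gives those categories as time windows: 4 to 12 weeks, and beyond 12 weeks.
- **Instruments** supplies graded 4-point symptom items from the C30 and LC29. Anosmia, ageusia and palpitation are checked for presence separately.
- Follow-up is at "3 (for those who are participated within 3 months of COVID diagnosis), 6, 9, and 12 months (T1-4"). Neither regression model is assigned to a visit.

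**The concern.** One power statement stands beside two models for aim 3. The effect measure f² is defined through the R² of a linear model, so the stated 80% has no direct meaning for a logistic regression. That model has no odds ratio, event rate or power of its own. The dropout step also looked short: multiplying by 1.2 does not restore 98 after a 20% loss.

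The existence outcome cannot be computed as written. The NICE windows do not separate cases from non-cases here, because every scheduled visit is already later than 4 weeks. What is missing is the response level that counts as present, how the graded items and the three extra symptoms combine, and the visit. The visit also affects the number analysed, since the 3-month assessment exists only for people enrolled within 3 months of diagnosis.

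At stake are a stated power that is slightly high for the one test it covers and absent for the other model, and outcome definitions that could be settled after the data are seen.

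**Working it through.** **1. Reproduce 98.** Inputs from Sampling and Recruitments: f² = 0.15, alpha = 0.05, target power 0.80, k = 6. For the omnibus test of R² = 0 in a linear regression, numerator df = 6, denominator df = N − 7, and noncentrality λ = f² × N.

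| N | λ = 0.15 × N | Power |
|---|---|---|
| 94 | 14.10 | 0.7824 |
| 97 | 14.55 | 0.7984 |
| 98 | 14.70 | 0.8035 |
| 118 | 17.70 | 0.8859 |

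The smallest N reaching 0.80 is 98, so the figure reproduces exactly. The alternatives tried do not give it: a single coefficient among six gives 55 (two-sided) or 43 (one-sided); alpha 0.025 gives 114 and alpha 0.10 gives 80; five predictors give 92 and seven give 103.

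**2. Dropout.** 98 × 1.2 = 117.6, rounded up to the plan's 118. A 20% loss from 118 leaves 118 × 0.8 = 94.4, about 94, with power 0.78. To keep 98: 98 / 0.8 = 122.5, so 123.

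**3. Single predictors in the linear model.** The 80% is for all six jointly. R² = 0.15 / 1.15 = 0.130. If six uncorrelated predictors share it equally, each has partial f² = (0.130 / 6) / (1 − 0.130) = 0.025, and power for one is 0.33 at N = 94 and 0.34 at N = 98. If one predictor carried the whole effect, 55 subjects would already give 80%. The omnibus figure therefore says nothing definite about any one predictor.

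**4. Logistic model.** The plan gives no odds ratio and no design prevalence, so these figures rest on assumptions. The only prevalence range is background literature in Symptom profile of Long COVID ("the incidence rate of Long COVID is between 20%-80"%). Two-sided alpha is 0.05 and N = 98 throughout.

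- *Smaller outcome class:* 0.2 × 98 = 19.6 at 20% or 80% prevalence, and 49 at 50%. Over six predictors that is 3.3 and 8.2 each.
- *Continuous predictor, odds ratio per SD, uncorrelated with the others:* power = Φ(√(98 × p(1 − p)) × ln OR − 1.96). For OR 2 and p = 0.5: √24.5 × 0.693 − 1.96 = 1.47, power 0.93. For OR 1.5 and p = 0.2: √15.68 × 0.405 − 1.96 = −0.35, power 0.36.
- *Binary predictor split 50/50, OR 2, p = 0.2:* event proportions 0.146 and 0.254 with 49 per group, power 0.27. At p = 0.5 (0.414 and 0.586) power is 0.40.

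The range is 0.27 to 0.93, depending on effect, prevalence and predictor type. The plan fixes none of the first two and does not name the six predictors.

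**The case against.** - *The calculation never claims to cover existence.* True: it names no outcome, and tying it to the linear model is an inference, though a tight one. But it is the only power statement, and the two parts of aim 3 are not ranked, so its scope should be written down.
- *Severity is just as undefined.* This stands. Statistical methods names no severity score, scale or visit, and the 3-month visit is incomplete for severity too. The remedy must cover both outcomes.
- *Existence is partly defined.* Also fair. The symptoms are listed in Table 1, and Instruments treats anosmia, ageusia and palpitation as Long COVID symptoms, so that they count is arguably implied. The response level and the visit are the real gaps.
- *A single visit may be too narrow.* Agreed. Predictors of Long COVID? speaks of different stages of survivorship, so the plan may properly use several visits if it names them.
- *Ordinary logistic regression is not an error.* Agreed. A reader might infer that a penalised fit is required. In simulation with six continuous predictors at N = 94 and 98, ordinary Wald intervals covered 94.3% to 96.0%, and the ordinary and Firth tests had practically the same power once both were calibrated to 5%.
- *Nothing in the plan treats a non-significant predictor as no association.* True. Asking for every confidence interval is good reporting, not correction of a stated error.

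**Conclusion.** The point holds, within limits. The 98 is right for the omnibus F test of a six-predictor linear model at f² = 0.15. With the plan's own 118 and 20% loss, that test has power of about 0.78, not 0.80: a small shortfall. The figure does not apply to the logistic model for existence or to single predictors in either model. The missing outcome definitions are a gap in detail and affect severity as well as existence.

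Two stronger readings are not supported. A reader might infer that the existence model is underpowered. The plan leaves its power undetermined: a large effect with prevalence near 50% would be adequately powered, and a moderate effect at 20% or 80% would not. A reader might also infer that the targeting of high-risk people described in Expecting outcomes rests on the existence model. That sentence concerns severe Long COVID, so it does not show this.

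The 0.78 needs only the plan's inputs and a full 20% loss. The 0.27 to 0.93 range rests on the assumed odds ratios, prevalences and predictor types shown in the working.

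**What to change.** **Sampling and Recruitments.** State that the calculation is for the omnibus test of the linear severity model only. Restate its power as about 0.78 for the 94 expected after 20% loss from 118 (98 after that loss would need 123). State that the logistic model for existence is not powered by it, and that the 80% does not apply to single predictors. Give no power figure for existence unless the prevalence, effect and test assumed are given with it.

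**Statistical methods.** Before analysis:
1. Define existence: which items or scales count, the response level that counts as present, whether the three separately checked symptoms count, and the visit or visits used.
2. Define the severity score and its visit or visits in the same way.
3. Note that the 3-month visit exists only for those enrolled within 3 months of diagnosis, and what that does to the number analysed.
4. Report every predictor in both models with its confidence interval.

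Firth's penalised likelihood is optional, for use if the smaller outcome class is sparse or separation occurs.

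**Cost.** Protocol wording only, with no change to recruitment or data collection. The price is a slightly lower stated power and an open statement that the existence analysis has not been sized.
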